5.3.5.6 Abnormal Vital Sign Values

Not every vital sign abnormality qualifies as an adverse event. A vital sign result must be reported as an adverse event if it meets any of the following criteria:

- Is accompanied by clinical symptoms
- Results in a change in study treatment (e.g., dosage modification, treatment interruption, or treatment discontinuation)
- Results in a medical intervention or a change in concomitant therapy
- Is clinically significant in the investigator's judgment

It is the investigator's responsibility to review all vital sign findings. Medical and scientific judgment should be exercised in deciding whether an isolated vital sign abnormality should be classified as an adverse event.

If a clinically significant vital sign abnormality is a sign of a disease or syndrome (e.g., high blood pressure), only the diagnosis (i.e., hypertension) should be recorded on the Adverse Event eCRF.

Observations of the same clinically significant vital sign abnormality from visit to visit should only be recorded once on the Adverse Event eCRF (see Section 5.3.5.4 for details on recording persistent adverse events).

5.3.5.7 Abnormal Liver Function Tests

The finding of an elevated ALT or AST ($>3 \times \text{ULN}$) in combination with either an elevated total bilirubin ($>2 \times \text{ULN}$) or clinical jaundice in the absence of cholestasis or other causes of hyperbilirubinemia is considered to be an indicator of severe liver injury (as defined by Hy's Law). Therefore, investigators must report as an adverse event the occurrence of either of the following:

- Treatment-emergent ALT or AST $>3 \times \text{ULN}$ in combination with total bilirubin $>2 \times \text{ULN}$
- Treatment-emergent ALT or AST $>3 \times \text{ULN}$ in combination with clinical jaundice

The most appropriate diagnosis or (if a diagnosis cannot be established) the abnormal laboratory values should be recorded on the Adverse Event eCRF (see Section 5.3.5.2) and reported to the Sponsor immediately (i.e., no more than 24 hours after learning of the event) either as a serious adverse event or an adverse event of special interest (see Section 5.4.2).

5.3.5.8 Deaths

For this protocol, mortality is an efficacy endpoint. Deaths that occur during the protocol-specified adverse event reporting period (see Section 5.3.1) that are attributed by the investigator solely to progression of MBC should be recorded on the Death Attributed to Progressive Disease eCRF. All other deaths that occur during the adverse event reporting period, regardless of relationship to study drug, must be recorded on the Adverse Event eCRF and immediately reported to the Sponsor (see Section 5.4.2).

Death should be considered an outcome and not a distinct event. The event or condition that caused or contributed to the fatal outcome should be recorded as the single medical concept on the Adverse Event eCRF. Generally, only one such event should be reported. If the cause of death is unknown and cannot be ascertained at the time of reporting, "**unexplained death**" should be recorded on the Adverse Event eCRF. If the cause of death later becomes available (e.g., after autopsy), "unexplained death" should be replaced by the established cause of death. The term "**sudden death**" should not be used unless combined with the presumed cause of death (e.g., "sudden cardiac death").

Deaths that occur after the adverse event reporting period should be reported as described in Section 5.6.

5.3.5.9 Preexisting Medical Conditions

A preexisting medical condition is one that is present at the screening visit for this study. Such conditions should be recorded on the General Medical History and Baseline Conditions eCRF.

A preexisting medical condition should be recorded as an adverse event only if the frequency, severity, or character of the condition worsens during the study. When recording such events on the Adverse Event eCRF, it is important to convey the concept that the preexisting condition has changed by including applicable descriptors (e.g., "more frequent headaches").

5.3.5.10 Lack of Efficacy or Worsening of Metastatic Breast Cancer

Events that are clearly consistent with the expected pattern of progression of the underlying disease should not be recorded as adverse events. These data will be captured as efficacy assessment data only. The expected pattern of progression will be supported by radiology assessments as per RECIST v1.1. In rare cases, the determination of clinical progression will be based on symptomatic deterioration. However, every effort should be made to document progression through use of objective criteria. If there is any uncertainty as to whether an event is due to disease progression, it should be reported as an adverse event.

5.3.5.11 Hospitalization or Prolonged Hospitalization

Any adverse event that results in hospitalization (i.e., inpatient admission to a hospital) or prolonged hospitalization should be documented and reported as a serious adverse event (per the definition of serious adverse event in Section 5.2.2), except as outlined below.

An event that leads to hospitalization under the following circumstances should not be reported as an adverse event or a serious adverse event:

- Hospitalization for respite care
- Planned hospitalization required by the protocol (e.g., to provide TLS prophylaxis or monitoring without significant clinical sequelae, or to perform an efficacy measurement for the study)
- Hospitalization for a preexisting condition, provided that all of the following criteria are met:
 - The hospitalization was planned prior to the study or was scheduled during the study when elective surgery became necessary because of the expected normal progression of the disease
 - The patient has not experienced an adverse event
- Hospitalization due solely to progression of the underlying cancer

An event that leads to hospitalization under the following circumstances is not considered to be a serious adverse event, but should be reported as an adverse event instead:

- Hospitalization that was necessary because of patient requirement for outpatient care outside of normal outpatient clinic operating hours

5.3.5.12 Adverse Events Associated with an Overdose or Error in Drug Administration

An overdose is the accidental or intentional use of a drug in an amount higher than the dose being studied. An overdose or incorrect administration of study treatment is not itself an adverse event, but it may result in an adverse event. All adverse events associated with an overdose or incorrect administration of study drug should be recorded on the Adverse Event eCRF. If the associated adverse event fulfills seriousness criteria, the event should be reported to the Sponsor immediately (i.e., no more than 24 hours after learning of the event; see Section [5.4.2](#)).

No safety data related to overdosing of venetoclax are available. Refer to the local fulvestrant package insert for safety information related to fulvestrant.

5.3.5.13 Patient-Reported Outcome Data

Adverse event reports will not be derived from PRO data by the Sponsor, and safety analyses will not be performed using PRO data. Sites are not expected to review the PRO data for an adverse event.

5.4 IMMEDIATE REPORTING REQUIREMENTS FROM INVESTIGATOR TO SPONSOR

Certain events require immediate reporting to allow the Sponsor to take appropriate measures to address potential new risks in a clinical trial. The investigator must report such events to the Sponsor immediately; under no circumstances should reporting take place more than 24 hours after the investigator learns of the event. The following is a list of events that the investigator must report to the Sponsor within 24 hours after learning of the event, regardless of relationship to study drug:

- Serious adverse events (defined in Section [5.2.2](#); see Section [5.4.2](#) for details on reporting requirements)
- Adverse events of special interest (defined in Section [5.2.3](#), see Section [5.4.2](#) for details on reporting requirements)
- Pregnancies (see Section [5.4.3](#) for details on reporting requirements)

The investigator must report new significant follow-up information for these events to the Sponsor immediately (i.e., no more than 24 hours after becoming aware of the information). New significant information includes the following:

- New signs or symptoms or a change in the diagnosis

- Significant new diagnostic test results
- Change in causality based on new information
- Change in the event's outcome, including recovery
- Additional narrative information on the clinical course of the event

Investigators must also comply with local requirements for reporting serious adverse events to the local health authority and Institutional Review Board (IRB)/Ethics Committee (EC).

5.4.2 Reporting Requirements for Serious Adverse Events and Adverse Events of Special Interest

5.4.2.1 Events That Occur prior to Study Drug Initiation

After informed consent has been obtained but prior to initiation of study drug, only serious adverse events caused by a protocol-mandated intervention should be reported. The paper Clinical Trial Serious Adverse Event/Adverse Event of Special Interest Reporting Form provided to investigators should be completed and submitted to the Sponsor or its designee immediately (i.e., no more than 24 hours after learning of the event), either by faxing or by scanning and emailing the form using the fax number or email address provided to investigators.

5.4.2.2 Events That Occur after Study Drug Initiation

After initiation of study drug, serious adverse events and non-serious adverse events of special interest will be reported through 28 days after the last dose of study drug. Investigators should record all case details that can be gathered immediately (i.e., within 24 hours after learning of the event) on the Adverse Event eCRF and submit the report via the electronic data capture (EDC) system. A report will be generated and sent to Roche Safety Risk Management by the EDC system.

In the event that the EDC system is unavailable, the paper Clinical Trial Serious Adverse Event/Adverse Event of Special Interest Reporting Form provided to investigators should

be completed and submitted to the Sponsor or its designee immediately (i.e., no more than 24 hours after learning of the event), either by faxing or by scanning and emailing the form using the fax number or email address provided to investigators. Once the EDC system is available, all information will need to be entered and submitted via the EDC system.

Instructions for reporting adverse events that occur more than 30 days after the last dose of venetoclax or fulvestrant are provided in Section [5.6](#).

5.4.3 Reporting Requirements for Pregnancies

5.4.3.1 Pregnancies in Female Patients

Female patients of childbearing potential will be instructed to immediately inform the investigator if they become pregnant during the study or within 28 days after the last dose of study drug. A paper Clinical Trial Pregnancy Reporting Form should be completed and submitted to the Sponsor or its designee immediately (i.e., no more than 24 hours after learning of the pregnancy), either by faxing or by scanning and emailing the form using the fax number or email address provided to investigators. Pregnancy should not be recorded on the Adverse Event eCRF. The investigator must discontinue study drug and counsel the patient, discussing the risks of the pregnancy and the possible effects on the fetus. Monitoring of the patient should continue until conclusion of the pregnancy. Any serious adverse events associated with the pregnancy (e.g., an event in the fetus, an event in the mother during or after the pregnancy, or a congenital anomaly/birth defect in the child) should be reported on the Adverse Event eCRF. In addition, the investigator will submit a Clinical Trial Pregnancy Reporting Form when updated information on the course and outcome of the pregnancy becomes available.

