3.3 END OF STUDY AND LENGTH OF STUDY

The study duration will be the time from screening of the first patient through 2 years after the last patient is enrolled, or all patients in the study have withdrawn consent or died, or if the study is prematurely terminated by the Sponsor, whichever occurs first. With enrollment anticipated to last approximately 18 months, the total length of the study is expected to be approximately 43 months.

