- For women of childbearing potential: agreement to remain abstinent (refrain from heterosexual intercourse) or use non-hormonal contraceptive methods with a failure rate of $< 1\%$ per year during the treatment period and for *up to 2 years* after the last dose of study drug (*or based on the local prescribing information for fulvestrant*). Women must refrain from donating eggs during this same period.

A woman is considered to be of childbearing potential if she is postmenarcheal, has not reached a postmenopausal state (≥ 12 continuous months of amenorrhea with no identified cause other than menopause), and has not undergone surgical sterilization (removal of ovaries and/or uterus).

Examples of non-hormonal contraceptive methods with a failure rate of $< 1\%$ per year include bilateral tubal ligation, male sterilization, and copper intrauterine devices.

The reliability of sexual abstinence should be evaluated in relation to the duration of the clinical trial and the preferred and usual lifestyle of the patient. Periodic abstinence (e.g., calendar, ovulation, symptothermal, or postovulation methods) and withdrawal are not acceptable methods of contraception.

- Willing to provide tumor biopsy sample
 - A tumor biopsy sample (either archival or fresh) must be collected from all patients from either the primary tumor or a metastatic site (if clinically feasible) for determination of expression of BCL-2 by central laboratory testing for patient eligibility purposes and for exploratory research on biomarkers. The tumor specimen must contain adequate evaluable tumor cells ($\geq 20\%$ tumor cells) to enable BCL-2 IHC and other relevant biomarker analysis. Samples can be in a tissue block (preferred) or prepared as 20 unstained serial slides, and should be accompanied by an associated pathology report. If a tumor sample is not available, a fresh biopsy must be collected. The specimen must be a formalin-fixed, paraffin-embedded (FFPE) tumor specimen, or another appropriate fixative must be used (notation of the type of fixative should be included). Cytological or fine-needle aspiration samples are not acceptable.
- Have at least one measurable lesion via RECIST v1.1.
 - Bone lesions that have been irradiated are not evaluable. Previously irradiated lesions can be considered as measurable disease only if progressive disease has been unequivocally documented at that site since radiation.

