4.5.5 Tumor and Response Evaluations

All known sites of disease must be assessed per RECIST v1.1 and documented at screening (within 28 days prior to Cycle 1 Day 1) and re-assessed at each subsequent tumor evaluation (every 8 weeks [± 5 days] from the date of randomization until Week 24 [± 5 days] and every 12 weeks [± 5 days] thereafter). Tumor assessments should be performed on this schedule regardless of dose delay until disease progression. In case of early discontinuation, only the patients who discontinue study treatment early without progression and who have not started follow-on treatment will remain on the study's schedule of assessments for progression. Patients who progress or discontinue early without progression but who have initiated a new treatment will remain on the study for OS.

Screening assessments must include computed tomography (CT)/magnetic resonance imaging (MRI) scans of the chest, abdomen, and pelvis; CT/MRI scans of the neck and brain imaging should be included if clinically indicated. A documented SOC tumor assessment performed within 28 days prior to Cycle 1 Day 1 may be used for the

screening assessment provided it meets the above requirements. CT scans should be performed with a contrast agent. For patients with known allergies to the contrast media, it is acceptable to perform a chest CT scan without contrast and an MRI scan for the abdomen (ideally at baseline and every tumor assessment thereafter).

If a CT scan for tumor assessment is performed in a positron emission tomography (PET)/CT scanner, the CT acquisition must be consistent with the standards for a full-contrast diagnostic CT scan.

Response assessment will be made by the investigator on the basis of physical examinations, CT scans, or MRI, and/or bone scans using criteria outlined in RECIST v1.1 ([Appendix 4](#)). The same radiographic procedure used to assess disease sites at screening should be used throughout the study (e.g., the same contrast protocol for CT scans). Assessments should be performed by the same evaluator to ensure internal consistency across visits.

CT scans throughout the study should include chest, abdomen, and pelvic scans. CT scans of the neck and brain imaging should be included if clinically indicated. At the investigator's discretion, CT scans may be repeated at any time if progressive disease (PD) is suspected.

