4.5.7 Laboratory, Biomarker, and Other Biological Samples

Samples for hematology, blood chemistries, and urinalysis will be analyzed at the study site's local laboratory. Samples for biologic markers and pharmacokinetics will be sent to one or more central laboratories or to the Sponsor or designee for analysis. Samples will be collected as per the schedule of activities in [Appendix 1](#).

Instruction manuals and supply kits will be provided for all central laboratory assessments.

Laboratory assessments will include the following:

- Hematology: hemoglobin, hematocrit, RBC count, platelet count, WBC count, and WBC differential count (neutrophils, bands [optional], lymphocytes, eosinophils, basophils, monocytes), and absolute counts
- Chemistry: sodium, potassium, chloride, random glucose, BUN, creatinine, ALT, AST, total bilirubin, amylase, lipase, total protein, albumin, calcium, phosphorus, LDH, CK, gamma-glutamyl transferase, alkaline phosphatase (ALP), and uric acid

To evaluate any possible risk of TLS with venetoclax in patients with ER-positive breast cancer, the first 10 patients enrolled into each arm will have a sample collected for a serum chemistry panel 24 hours after the first dose of study drug.

- Coagulation: INR or aPTT (or PTT) required for all patients within 14 days prior to Cycle 1 Day 1 and then as clinically indicated
- Urinalysis: Specific gravity, pH, glucose, protein, ketones, and blood
Urinalysis is required for all patients within 28 days prior to Cycle 1 Day 1 and then as clinically indicated
- Viral serology: hepatitis B (HBsAg) or hepatitis C (HCV antibody)
Patients who are positive for HCV antibody must be negative for HCV by PCR to be eligible for study participation.
Patients with a past or resolved HBV infection (defined as having a positive total HBcAb and negative HBsAg) may be included if HBV DNA is undetectable. These patients must be willing to undergo monthly DNA testing.
- Pregnancy test:

Women of childbearing potential (defined in Section 4.1.1) must have a negative serum pregnancy test result at screening within 14 days prior to the first study drug administration.

The urine pregnancy tests should be repeated during the treatment period within 3 days prior to each cycle (every 28 days starting on Day 1 of Cycle 2), at the study discontinuation visit, and as clinically indicated.

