5.1.1.5 Reproductive System Effects and Pregnancy

This study enrolls only female patients. The effect of BCL-2 inhibition on pregnancy has not been fully characterized. In animal studies, venetoclax resulted in increased post-implantation loss, and decreased fetal body weights were observed in the mouse embryo-fetal development study at the highest dosage administered. Venetoclax was not teratogenic.

Two human pregnancies have been reported in the clinical program with venetoclax so far, including one pregnancy of a partner; in both cases, a live infant with no neonatal complication, congenital anomalies, or birth defects was delivered.

In nonclinical studies, both venetoclax and fulvestrant have shown a potential to cause reproductive and embryo-fetal developmental toxicities as single agents. Therefore, there is the potential for this combination to cause overlapping or additional reproductive and embryo-fetal toxicities than the individual molecules. Consequently, both venetoclax and fulvestrant should not be administered to pregnant women, and they must be discontinued if a patient becomes pregnant. Additionally, patients are advised to remain abstinent (i.e., refrain from heterosexual intercourse) or use non-hormonal contraceptive methods with a failure rate of < 1% per year during the treatment period and for *up to 2 years after the last dose of study drug (or based on the local prescribing information for fulvestrant)*. Please refer to Section 4.1.1 for further details on study eligibility and contraceptive requirements for patients.

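### The pregnancy reporting period in Section 5.4.3.1 is not aligned with the contraception period after last dose, and its reach depends on an undefined term

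*Combined protocol and SAP*

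**What the plan says.** - **Contraception.** Section 4.1.1 requires abstinence or non-hormonal contraception during treatment and "for *up to 2 years* after the last dose of study drug", with local fulvestrant prescribing information as the alternative. The synopsis and Section 5.1.1.5 ("up to 2 years after the last dose of study drug") agree. Section 5.1.1.5 gives the reason: "both venetoclax and fulvestrant have shown a potential to cause reproductive and embryo-fetal developmental toxicities as single agents", and the combination may add to this.
- **Pregnancy reporting.** Under Section 5.4.3.1 patients are told to inform the investigator "if they become pregnant during the study or within 28 days after the last dose of study drug".
- **Pregnancy testing.** Section 4.5.7 has urine tests before each cycle from Cycle 2, then "at the study discontinuation visit, and as clinically indicated". Section 4.6.1 places that visit 28 days (+3) after last dose. Appendix 1 schedules no test in off-treatment or survival follow-up.
- **Follow-up.** Section 4.5.5 says patients who progress, or who stop early and start another treatment, "will remain on the study for OS". Section 3.3 runs the study "through 2 years after the last patient is enrolled", unless all patients have withdrawn or died, or the sponsor ends it sooner.

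**The concern.** The protocol treats a period of up to 2 years after last dose as one in which pregnancy should be avoided because of possible harm to the fetus. Its instruction to report a pregnancy is tied to a different and possibly much shorter period. The 28 days match the general adverse event reporting period in Section 5.3.1, not the contraception period.

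What is at stake is the completeness of safety data. A pregnancy that begins inside the protocol's own period of concern but outside the reporting instruction may never reach the sponsor. It would then not be followed to outcome, since Section 5.5.1 follows only pregnancies reported during the study.

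**Working it through.** The plan states no figure to reproduce. The check compares the two periods under each meaning that *during the study* can carry.

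**Inputs from the documents:** contraception window W of up to 2 years (730.5 days); fixed reporting window of 28 days; accrual of about 18 months; study end 24 months after the last patient is enrolled (Section 3.3).
**Assumptions, not in the documents:** shorter local labelling periods of 1 year and 6 months; median treatment durations of 2 to 12 months.

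**Reading A: the phrase means the treatment period.** Share left out = (W − 28)/W.
- 2 years: (730.5 − 28)/730.5 = 702.5/730.5 = 96.2%
- 1 year (assumed): (365.25 − 28)/365.25 = 92.3%
- 6 months (assumed): (182.6 − 28)/182.6 = 84.7%

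**Reading B: the phrase includes follow-up to study end.** Let L be the date of last dose and E the date the last patient is enrolled. The 2-year window ends at L + 24 months and the study at E + 24 months. The part left out is therefore (L + 24) − (E + 24) = L − E, with a floor of zero and a ceiling of 24 months less 28 days (24 − 0.92 = 23.08 months). Two results need no assumption about treatment duration:
- A patient whose last dose falls on or before the day the last patient is enrolled is fully covered.
- A patient dosed up to study end has only the 28 days, 28/730.5 = 3.8% of the window, as under reading A.

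For the average over patients, take uniform accrual over 18 months and exponential time to last dose with rate λ = ln 2/median. Ignore deaths, withdrawals and early termination.
- Mean months left out = (1 − e^(−18λ))(1 − e^(−23.08λ))/(18λ²)
- Share of patients with under half the window covered = e^(−12λ)(1 − e^(−18λ))/(18λ)

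For a 12-month median, λ = 0.0578. The mean left out is about 7.9 months, so 1 − 7.9/24 = 67% is covered. A simulation of 400,000 patients gave:

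| Assumed median treatment (months) | Mean share of 2-year window covered | Patients with under half covered |
|---|---|---|
| 2 | 98% | 0.2% |
| 4 | 93% | 4% |
| 6 | 86% | 11% |
| 9 | 76% | 21% |
| 12 | 67% | 31% |

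**Patients the current amendment still governs.** Section 6.4 sets the primary analysis at 6 months after last patient in, or when all patients are off treatment if sooner. The cut-off was 5 August 2020 (Section 1.4). If patients were still on treatment and the cut-off fell at 6 months, E is about February 2020. The documents do not state this date. A patient still on treatment on 8 October 2020 would then have L − E of about 8 months or more left out under reading B, if the 2-year period applies to her.

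**Other routes set beside the gap.**
- Section 5.4 requires investigators to report pregnancies within 24 hours of learning of them. It states no time limit, but refers to Section 5.4.3 for details.
- Section 5.4.3.3 makes birth defects in a child of an exposed patient reportable, with no limit stated.
- Section 5.4.3.2 makes spontaneous abortion a serious adverse event. Both subsections refer to Section 5.4.2, whose general period is 28 days.
- Section 5.6 covers later serious adverse events believed related to study drug.

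All of these depend on the investigator hearing of the event. Survival follow-up under Section 4.6.1 may be by telephone or from records, and collects survival and new therapy. Pregnancy itself is not recorded as an adverse event (Section 5.4.3.1).

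**The case against.** The strongest objection is that the instruction contains an *or*. Patients in survival follow-up are described as still on the study, so on the literal wording most of the 2-year window is covered for most patients. This stands. A reader might infer that most of the protocol's own risk window goes unreported, but the documents support that only if the phrase means the treatment period, which Section 5.4.3.1 does not say.

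A reader might answer that counting follow-up would leave the 28-day clause with no purpose. That goes too far. The clause would still serve patients dosed close to study end, or whose participation stops early through withdrawal or sponsor termination. The clause and the end of scheduled testing at the discontinuation visit lend reading A some support, but do not settle it.

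Nor do the documents support saying that late birth defects or abortions would never be reported, given the routes in Sections 5.4.3.2, 5.4.3.3 and 5.6. It is also fair that 2 years is an upper limit, that few pregnancies are expected (patients are postmenopausal or on an LHRH agonist), and that the documents nowhere require the two periods to match.

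What the objection leaves standing is that the term is undefined, no section aligns the periods, and patients treated late fall outside the instruction on either reading.

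**Conclusion.** The concern holds as a misalignment between sections together with an undefined term. The part of the contraception window left out ranges from nothing (reading B, last dose by the time enrolment closes) to about 96% of 2 years (reading A for every patient, or reading B for someone treated to study end). Under reading B, mean coverage is 67% to 98%, which rests on the assumed treatment durations and on ignoring deaths, withdrawals and early termination. If local labelling sets a shorter period, the gap shrinks; the documents do not give that figure.

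The events without a clear route are late pregnancies that end normally or in an outcome not attributed to drug. Their number should be small. The effect is on the completeness of safety data; the efficacy endpoints, analyses and sample size are untouched.

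**What to change.** Reconcile Section 5.4.3.1 with Sections 4.1.1 and 5.1.1.5. The instruction to report a pregnancy should cover the contraception period that applies to the patient, including any part that falls after study end. Either define *during the study* or replace it with a period counted from last dose. Tell patients of the period at the discontinuation visit, and check that the consent text agrees. This review takes no view on which contraception period is right.

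The cost is a short wording change and at most a few additional reports, with some provision for receiving reports after the study closes. No visit, test or analysis needs to be added.
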